10.6 Rescue medication

During Part 1 (Treatment Period) only, morphine oral solution will be supplied by the sponsor as rescue medication for both treatment groups.

An interactive response technology system (voice and web based) will be used to assign subjects to rescue medication.

Name:	Morphine oral solution
Substance name:	Morphine sulfate or morphine hydrochloride
Active component(s):	Morphine
Dose (strength):	0.5% and/or 2.0%
Final release of the re-packaged product:	Grünenthal GmbH, Aachen, Germany

During Part 2, the use of immediate release strong opioids for treatment of breakthrough pain and incidental pain is allowed.

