10.6.1 Dose

The dose of morphine oral solution per intake of rescue medication is ~1/6 of the total daily dose of morphine PR treatment or ~1/6 of the morphine equivalent dose of tapentadol PR treatment.

The investigators and parent or legal guardian of the subject will be provided with a table showing clearly what dose of morphine oral solution the subject should take as rescue medication.

Subjects on the highest dose of IMP are not allowed to take more than 4 doses of rescue medication per day on 2 consecutive days as this indicates a lack of efficacy (defined as a discontinuation criteria, see Section 9.3.1). No more than 10 doses of rescue medication at any dose level are allowed per day.

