10.7 Documentation of drug accountability

For tapentadol PR and morphine PR tablets, drug accountability must be performed on a tablet basis per assigned IMP kit.

The bottles of rescue medication oral solution (morphine) will be weighed using appropriately calibrated scales before handing out to the subject/parent or legal guardian and at return to allow drug accountability.

The investigator is obliged to keep documentation of the receipt, inventory, use, and destruction or return of unused, used, or partially used packages of trial treatment(s). The documentation must include trial treatment name, dates, quantities, subject numbers, batch/serial numbers or other identification numbers, expiration dates, and the means to identify the subject to whom it was given.

In addition to records in the documentation, e.g., source documents, CRF, the investigator must maintain documentation of drug accountability, i.e., separate records of the subject's numbers, date of dispensing, and amount of trial treatment(s) dispensed to each subject and returned by each subject, and the return date.

Before the unused IMPs and other medications supplied to the investigator are returned or destroyed, the investigator must allow sponsor representatives to perform drug reconciliation. The entries in the documentation will be compared with the returned and residual trial treatment(s), and the administration/intake as documented in the CRF, with clarification of any discrepancies or inconsistencies. The documentation should also be checked regarding the expected amount to be returned according to the expected treatment dose.

See Section 12.8 for compliance limits.

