14.2.6.3 Rescue medication

The descriptive analyses of the use of rescue medication during the Treatment Period will focus on mean number of daily doses and the mean total daily dose (mg/kg). The morphine equivalent dose of tapentadol will be calculated so that a comparison of rescue medication with respect to the amount of IMP taken can be made. Comparisons will be made across time and also for subgroups of different ages.

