13.3.2 Rescue medication

The analyses of rescue medication address only Part 1. Rescue medication is assessed in the eDiary and assessed in the drug accountability page of the eCRF.

Analyses based on eDiary-data:

For each day of the Treatment Period (day 1 until day 16) the two endpoints

- Number of daily doses.
- Total daily dose (mg/kg).

will be summarized descriptively and compared to the mean amount of IMP (morphine equivalent) within the treatment arms of that day. The individual daily amount of IMP will be compared over time to the two endpoints with Pearson's and Spearman's correlation coefficients (see [Section 18.1.9](#) for details).

In addition, descriptive statistics will be presented for the subgroups as specified in [Table 4](#).

The time from first IMP to first rescue medication intake will be summarized using time-to-event methods. The calculation of time to first rescue medication and the censoring algorithm are described in [Section 18.1.9](#).

The percentage of days with rescue medication intake will be summarized descriptively as a categorical variable using the following percentage categories: 0, (0-10), [10-20), [20-30), ..., [90-100), 100. The percentages will be calculated considering the day of the first IMP intake up to the day of the last IMP intake of Part 1 (both included).

Analyses based on eCRF-data:

Based on information in the drug accountability page of the eCRF, the average mean daily dose for each subject, i.e., the cumulative volume difference between Visit V2 and Visit VE divided by the number of days between Visit V2 and Visit VE (both days included), will be analyzed descriptively.

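### The eCRF-based rescue dose is defined as volume per day, so it is not in mg/kg and, if both permitted solution strengths are used, equal morphine doses give values four-fold apart

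*SAP*

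**What the plan says.** SAP 13.3.2 has two sources for rescue medication in Part 1. From the eDiary it summarises the number of daily doses and the total daily dose in mg/kg. From the drug accountability page of the eCRF it summarises an average daily dose for each subject, defined as "the cumulative volume difference between Visit V2 and Visit VE divided by the number of days between Visit V2 and Visit VE". The second definition equates a dose with a volume per day. The rescue programming section, SAP 18.1.10, adds nothing on this measure.

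The protocol text that bears on it:

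- Protocol 10.6 gives the strength of the oral solution as 0.5% and/or 2.0% and the substance as "Morphine sulfate or morphine hydrochloride". On supply it says: "An interactive response technology system (voice and web based) will be used to assign subjects to rescue medication". The current text gives no rule for which strength a child receives.
- Protocol 10.6.1 sets the rescue dose in terms of morphine, not volume: "The dose of morphine oral solution per intake of rescue medication is ~1/6 of the total daily dose of morphine PR treatment", or about the same fraction of the morphine equivalent of tapentadol PR.
- Protocol 10.6.3 has each intake recorded in the diary in mg.
- Protocol 10.7 says what is measured for accountability: "The bottles of rescue medication oral solution (morphine) will be weighed using appropriately calibrated scales", at hand-out and again at return.
- Protocol 14.2.6.3 names the planned rescue measures as "mean number of daily doses and the mean total daily dose (mg/kg").

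**The concern.** A volume is a dose only after it is multiplied by a concentration. With two permitted concentrations and no conversion, the derived value depends on the bottle as well as on the morphine taken. The unit also differs from the mg/kg of the protocol and of the diary-based analysis.

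The omission is specific to rescue medication. For IMP, SAP 18.1.7 multiplies tablets dispensed and returned by the mg per tablet of each kit, and SAP 12.1 reports the accountability-based daily dose of Part 1 per kg body weight. Rescue has neither step.

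What is at stake is the reading of one table. Rescue is morphine in both arms, morphine is also the comparator, and the responder definition sets no limit on rescue. A reader will therefore want to compare supplementary morphine between arms. The accountability summary is the SAP's only rescue summary that does not rest on diary entries, and as written it cannot be laid beside the diary result.

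**Working it through.** The documents give no numerical figure for this measure, so there is none to reproduce. The check is direct arithmetic.

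**Inputs**

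- Strengths 0.5% and 2.0% (Protocol 10.6). Reading them as weight per volume gives 5 and 20 mg/mL. This is an assumption. The ratio between them needs only that both percentages are on the same basis.
- Rescue dose per intake about 1/6 of the total daily morphine PR dose (Protocol 10.6.1).
- Total daily morphine PR dose from 2 × 10 = 20 mg to 2 × 100 = 200 mg (Protocol Table 3).

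**Equal dose, two bottles.** Volume = mg / concentration, so the ratio of volumes for equal mg is 2.0 / 0.5 = 4.0.

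| Morphine taken | 0.5% solution | 2.0% solution |
|---|---|---|
| 20 mg/day | 20 / 5 = 4.0 mL/day | 20 / 20 = 1.0 mL/day |
| One intake, 20 / 6 = 3.33 mg | 0.667 mL | 0.167 mL |
| One intake, 200 / 6 = 33.3 mg | 6.667 mL | 1.667 mL |

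**Order can reverse.** A subject on 20 mg/day from the 0.5% bottle scores 20 / 5 = 4.0 mL/day. A subject on 60 mg/day from the 2.0% bottle scores 60 / 20 = 3.0 mL/day. The smaller dose gives the larger value.

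**Group means.** Suppose every subject takes 20 mg/day and a share f is on the 0.5% solution. The mean is 4.0f + 1.0(1 − f) mL/day:

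| f | 0 | 0.25 | 0.5 | 0.75 | 1 |
|---|---|---|---|---|---|
| Mean mL/day | 1.0 | 1.75 | 2.5 | 3.25 | 4.0 |

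The mean dose is 20 mg/day in every column. Under the same simplification, two arms with the same share f have equal mean volumes, and arms with different shares do not. The documents do not give f, so this is a range and not an estimate for this trial.

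**After conversion.** 4.0 mL × 5 mg/mL = 20 mg and 1.0 mL × 20 mg/mL = 20 mg, so the ratio is 1.0. Dividing by body weight gives mg/kg/day.

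**Two further steps are missing.** Bottles are weighed, so a weight difference must be divided by a density to become a volume, and the SAP gives no such step. Two salts are permitted, and no common basis for mg of morphine is stated.

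**The case against.** Much of the case on the other side stands.

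- **It is one supplementary table.** Protocol 8.1.3 lists rescue use among the other endpoints, and no decision rests on it. The measures planned in Protocol 14.2.6.3 are delivered from the diary, which records mg. This stands, and it limits the reach of the point.
- **Both strengths may never be used.** The protocol permits them without requiring both. This stands: with a single strength the four-fold effect does not arise, and only the unit, label and per-kg problems remain.
- **Dose may be shorthand for a converted quantity.** The accountability page of the eCRF is not among the documents, so it might capture strength or convert weight. That is possible, but the SAP spells the measure out as a volume divided by days, and a programmer following it would produce mL/day. This does not remove the point.

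A reader might go further and infer that this summary is the main evidence on whether non-inferiority was reached with equal supplementary morphine, or the only objective check on the diary. The documents support neither. They give the summary no such role. Protocol 11.1.1 has sites confirm at Visits V3 and VE whether the returned rescue medication matches the expected amount and clarify discrepancies with the family, and Protocol 10.7 adds reconciliation of returned treatment against documented intake.

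**Conclusion.** The definition should be corrected. Followed literally, it gives a quantity that is not a dose. If both strengths are in use, equal morphine doses differ by a factor of 4.0 between subjects, and group means can lie anywhere from 1.0 to 4.0 mL/day at a common 20 mg/day. If one strength is in use, the result is mL/day labelled as a dose and is not comparable with the diary mg/kg.

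The factor of 4.0 rests on both percentages sharing a basis and on both strengths being used. The mL figures also assume weight per volume.

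It is tempting to quote a percentage distortion between the arms. That would need the mix of strengths in each arm, its relation to the child's dose, and the spread of doses, and the documents supply none of the three.

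The diary-based rescue analyses, the primary endpoint and the sample size are unaffected.

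**What to change.** Replace the definition in SAP 13.3.2, with the derivation in SAP 18.1.10, by:

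*eCRF rescue dose = sum over bottles of [(weight at hand-out − weight at return) / solution density × strength of that bottle] / number of days / body weight, in mg/kg/day.*

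State the density used, state whether mg refers to the sulfate or the hydrochloride and how the other is converted, and use the same body weight as the diary-based mg/kg measure. Report the result beside the diary-based mg/kg/day.

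Before this is adopted, the sponsor should confirm that the strength of each dispensed bottle can be retrieved. The protocol says that the response system assigns rescue medication but does not list what it stores. If strength cannot be retrieved, call the result a volume and present it by strength where known.

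The cost is a few lines in the SAP and one additional variable in the programming. If bottle strength is traceable, no new data are collected. The change concerns analysis only and does not touch how rescue medication is dosed or supplied.

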13.4 Acceptability and palatability

The acceptability and palatability questionnaire consists of two dimensions (taste/swallowing). The response to each dimension is measured on an ordinal, five-category scale.

For each of the two visits (Visit V3 and VE) and each of the two dimensions, responses will be summarized with descriptive statistics. The change between the two visits will be displayed for each dimension in a shift table.

In addition, descriptive statistics will be presented for the subgroups as specified in [Table 4](#).

14 ANALYSIS OF PHARMACOKINETIC AND PHARMACODYNAMICS PARAMETERS

Blood samples for serum pharmacokinetics are only taken from the tapentadol arm during Part 1 of the trial. Thus all subsequent elaborations only refer to the tapentadol arm of the Treatment Period of Part 1.

Descriptive statistics of the observed concentrations of tapentadol and tapentadol-O-glucuronide at the respective time points will be presented for all subjects and for subgroups as specified in [Table 4](#). The concentrations will be descriptively summarized by

- N>LLOQ (lower limit of quantification).
- Arithmetic mean, standard deviation and coefficient of variation.
- Geometric mean, standard deviation and coefficient of variation.

In addition, the data will be graphically displayed:

- Boxplots of plasma concentrations of tapentadol and tapentadol-O-glucuronide (on linear scale) by subgroups as specified in [Table 4](#).
- Mean plasma concentration and 95% confidence interval of tapentadol and tapentadol-O-glucuronide (on linear scale) by subgroups as specified in [Table 4](#).

The bioanalytical methods for the determination of individual serum concentrations of tapentadol and tapentadol-O-glucuronide will be reported together with the serum concentration results in separate bioanalytical reports. These bioanalytical reports will be appended to the ICTR.

A population pharmacokinetic/pharmacodynamic analysis will be performed using a non-linear mixed-effect modeling approach to investigate the pharmacokinetic properties, the correlation between drug exposure and therapeutic effect, concerned tolerability and safety aspects of the tapentadol and tapentadol-O-glucuronide. A pharmacometric analysis plan will be written before data base lock, and the pharmacokinetic/pharmacodynamic results will be reported separately from the ICTR. Therefore, the population pharmacokinetic/pharmacodynamic analysis is not subjects of this SAP.

15 SAFETY ANALYSES

No statistical tests for comparison of safety data between treatment arms will be performed.

Safety data will be summarized descriptively as described in Section [8.1](#).

All safety data will be presented for the SAF unless otherwise specified.

Unless otherwise specified, separate descriptive analyses will be performed for the different trial periods and respective treatment groups.

15.1 Secondary endpoint

The main secondary endpoints are:

Part 1

Constipation as assessed by changes from baseline of total scores for the modified constipation assessment scale (mCAS).

Part 1 and Part 2

Tolerability as assessed by the number and type of adverse events and adverse drug reactions by treatment arm during the different trial periods, on a subject and event level.

15.1.1 Constipation assessed by the modified constipation assessment scale

The assessment of constipation is considered a secondary endpoint for Part 1. For Part 2 it is considered an exploratory endpoint and its analysis is addressed in Section [15.2.6](#).

Descriptive summaries of each time point and summaries of the changes from baseline to Visit V3 and from baseline to Visit VE will be provided for the total score as well as each item.

15.1.2 Adverse events

Definition of non-treatment emergent adverse events (non-TEAE)

- All adverse events occurring during the pre-treatment Period (defined in Section [8.2.2](#)) are defined as pre-treatment non-TEAEs.
- All adverse events occurring during the post-Treatment Period (defined in Section [8.2.2](#)) are defined as post-treatment non-TEAEs.

Definition of treatment emergent adverse events (TEAE)

- All adverse events occurring or worsening on-treatment in one of the trial periods (defined in Section [8.2.2](#)) are defined as TEAEs of this period. Due to the consideration of the therapeutic reach in the definition of the on-treatment period, a TEAE that occurred during the on-treatment period of the Treatment or Tapentadol Period will be assigned to this trial period, although it actually might have started during the Observation Period.

The assessment whether an AE is a TEAE or a non-TEAE will be based on the start time of the AE recorded on the Adverse Event page of the eCRF. In case of partial dates or times, this assessment is done after imputation of missing date/time information; an AE will be considered treatment emergent unless the information available will clearly exclude it. For details on the imputation of missing date/time and programming aspects of adverse events in general, see Section [18.1.11](#).

15.1.2.1 Analyses of adverse events

The following overview tables of TEAEs will be generated as described in Section [8.1](#) for Part 1 and the Tapentadol Period of Part 2. For Part 1, in addition to the presentation by treatment arm, descriptive summaries will also be presented overall.

1. Summary of the number and percentage of subjects with at least one:

- TEAE.
- Serious TEAE.
- Non-serious TEAE.
- Unexpected TEAE.
- Related TEAE.
- Related serious TEAE.
- TEAE leading to discontinuation from IMP.
- TEAE leading to discontinuation from the trial.
- Deaths.

For Part 1 in addition:

- TEAE of Part 1, that are ongoing during the Tapentadol Period of Part 2.
- TEAE of Part 1, that are ongoing during the Observation Period of Part 2.
- TEAE of Part 1, that actually started during the Observation Period of Part 2 (within the therapeutic reach of the last IMP intake of the Treatment Period).

For Tapentadol Period of Part 2 in addition:

- TEAE of Part 1, that are ongoing during the Tapentadol Period of Part 2
- TEAE of Tapentadol Period of Part 2, that actually started during the Observation Period of Part 2 (within the therapeutic reach of the last IMP intake of the Tapentadol Period)
- TEAE of Tapentadol Period of Part 2, that are ongoing during the Observation Period of Part 2

2. Summary presenting the number of TEAEs per subject categorized as 0, 1, 2, 3, 4, 5, and >5.
3. Summary of the number and percentage of TEAEs for:
 - TEAEs.
 - Serious TEAEs.
 - Non-serious TEAEs.
 - Unexpected TEAE.
 - Related TEAEs.
 - Related serious TEAEs.
 - TEAE leading to discontinuation from IMP.
 - TEAE leading to discontinuation from the trial.

For Part 1 in addition:

- TEAE of Part 1, that are ongoing during the Tapentadol Period of Part 2.
- TEAE of Part 1, that are ongoing during the Observation Period of Part 2.
- TEAE of Part 1, that actually started during the Observation Period of Part 2.

For Tapentadol Period of Part 2 in addition:

- TEAE of Part 1, that are ongoing during the Tapentadol Period of Part 2.

- TEAE of Tapentadol Period of Part 2, that actually started during the Observation Period of Part 2.
- TEAE of Tapentadol Period of Part 2, that are ongoing during the Observation Period of Part 2.

The percentage denominator will be the total number of TEAEs.

In addition, these overview tables will be presented for subgroups as specified in [Table 4](#).

15.1.2.2 Incidence, Incidence Rates and number of events

The incidence of an AE is defined as the number of subjects with occurrence of this AE during the period of interest (pre-treatment, on-treatment or post-treatment).

The incidence rate (CIR for crude incidence rate) of an AE is defined as the number of subjects with occurrence of this AE during the period of interest divided by the total number of subjects n in the respective arm (defined in Section [8.1](#)).

Analysis by Preferred Term

For Part 1 and the Tapentadol Period of Part 2, for TEAEs with an incidence rate of $\geq 5\%$ in at least one of the arm displayed, the incidence, incidence rate, the number of events and the percentage of events (related to the total number of events) will be summarized by Preferred Term (PT), sorted by decreasing incidence rate in the arm of subjects randomized to tapentadol.

Percentages will be calculated related to the total number of subjects/events presented in the table, i.e., the number of subjects with TEAEs and the total number TEAEs for the respective trial Period.

Analysis by System Organ Class and Preferred Term

For Part 1 and the Tapentadol Period of Part 2, the incidence, incidence rate, the number of events and the percentage of events (related to the total number of events) will be summarized by System Organ Class (SOC) and PT (sorted alphabetically) for each

- TEAEs.
- Serious TEAEs.
- Non-serious TEAEs.
- Related TEAEs.

In addition, for TEAEs, the incidence, incidence rate, the number of events and the percentage of events will be summarized by SOC and PT for the subgroups as specified in [Table 4](#).

For serious TEAEs, the incidence, incidence rate, the number of events and the percentage of events will also be presented for serious related TEAEs, serious fatal TEAEs and serious fatal related TEAEs.

Percentages will be calculated related to the total number of subjects/events presented in the respective table e.g., for the presentation of SOC and PT for serious TEAEs percentages will be related to the number of subjects with serious TEAE/the total number of serious TEAEs, respectively.

For serious TEAEs, percentages will additionally be presented related to the total number of all subjects/events, respectively.

The incidence, incidence rate, the number of events and the percentage of events (related to the total number of events) will be summarized by SOC and PT (sorted alphabetically) for each

- Pre-treatment (Part 1 only, all enrolled subjects, by treatment arm and overall)
 - Non-TEAE.
 - Serious non-TEAE.
- Post-treatment (all trial Periods together, SAF, presenting the arms of the Observation Period)
 - Non-TEAE.
 - Serious non-TEAE.

Percentages will be calculated related to the total number of subjects/events presented in the respective table as outlined above for the TEAE tables by SOC and PT.

Analysis by System Organ Class, Preferred Term and descriptors

For Part 1 and the Tapentadol Period of Part 2, the number and percentage of events will be summarized by SOC and PT (sorted alphabetically) for the following AE descriptors. Presentations will be for TEAEs only.

- Intensity: mild, moderate, severe.
- Causal relationship to the IMP: related (with subcategories: possible, probable/likely, certain), not related (with subcategories: not related, unlikely), unknown (with subcategories: conditional/unclassified, assessable/unclassifiable, causal relationship missing).
- Outcome: recovered/resolved, recovering/resolving, not recovered/not resolved, recovered/resolved with sequelae, fatal, unknown.
- Non IMP related countermeasures: none, newly started medication, trial discontinuation, others.
- Action taken with IMP: dose increased, dose reduced, drug interrupted, drug withdrawn, dose not changed, not applicable, unknown.
- Measures of location and variation will be calculated for:
- Duration of TEAEs: Duration will be analyzed in days with measures of dispersion and variation.
- Time to onset of TEAE will be analyzed in days with measures of dispersion and variation.

Denominator for percentage calculation will be the number of all TEAEs for presentation over all SOCs, and the number of TEAEs per SOC or PT respectively for the presentation per SOC and PT, respectively.

The number and percentage of all post-treatment non-TEAEs (all Periods together) will be summarized by SOC and PT (sorted alphabetically) for the following AE descriptors:

- Intensity.
- Time to onset of post-treatment non-TEAEs after last IMP administration will be summarized with measures of dispersion and variation.

Listings

The following listings will be produced for all enrolled subjects:

- Deaths.
- Serious adverse events other than death.
- AEs leading to discontinuation from the trial.
- AEs leading to discontinuation from IMP.
- AEs leading to IMP dose decrease or interruption of IMP.
- AEs starting on the day of Visit VE (including the last IMP intake of Part 1 and first IMP intake of Part 2 [eDiary and dispense information]).

